9.2. Adverse Event

9.2.1. Definition of Adverse Event

An AE is any untoward medical occurrence in a subject administered a pharmaceutical product and that does not necessarily have to have a causal relationship with this treatment. An AE can therefore be any unfavorable and unintended sign (including an abnormal laboratory finding, for example), symptom, or disease temporally associated with the use of a medicinal product, whether or not considered related to the medicinal product (International Conference on Harmonisation [ICH] E2A Guideline. Clinical Safety Data Management: Definitions and Standards for Expedited Reporting, October 1994).²³

It is the responsibility of Investigators, based on their knowledge and experience, to determine those circumstances or abnormal laboratory findings which should be considered AEs.

9.2.2. Serious Adverse Event

An SAE is any untoward medical occurrence that at any dose:

- Results in death,
- Is life-threatening,
- Requires inpatient hospitalization or prolongation of existing hospitalization,
- Results in persistent or significant disability/incapacity,
- Is a congenital anomaly/birth defect, or
- Is an important medical event.

Note: A serious adverse event (SAE) is defined as an adverse event that is life-threatening, results in death, requires inpatient hospitalization or prolongation of existing hospitalization, results in persistent or significant disability/incapacity, is a congenital anomaly/birth defect, or is an important medical event. A serious adverse event does not refer to an event which hypothetically might have caused death if it were more severe (ICH E2A Guideline. Clinical Safety Data Management: Definitions and Standards for Expedited Reporting, October 1994).²³

Medical and scientific judgment should be exercised in deciding whether expedited reporting is appropriate in other situations, such as important medical events that may not be immediately life-threatening or result in death or hospitalization but may jeopardize the subject or may require intervention to prevent 1 of the other outcomes listed in the definition above. Examples include allergic bronchospasm, convulsions, and blood dyscrasias or development of drug dependency or drug abuse.

Note:

Procedures are not AEs or SAEs, but the reason for the procedure may be an AE or SAE.

Pre-planned (prior to signing the ICF) procedures or treatments requiring hospitalizations for pre-existing conditions that do not worsen in severity are not SAEs.

9.2.3. Severity Assessment

All AEs will be graded (1 to 5; see below) according to the latest NCI-CTCAE.²⁴

Grade 1 Mild AE

Grade 2 Moderate AE

Grade 3 Severe AE

Grade 4 Life-threatening consequences; urgent intervention indicated

Grade 5 Death related to AE

Severity vs. Seriousness: Severity is used to describe the intensity of a specific event while the event itself, however, may be of relatively minor medical significance (such as severe headache). This is not the same as "seriousness," which is based on subject/event outcome at the time of the event. For example, the NCI-CTCAE Grade 4 (life-threatening consequences; urgent intervention indicated) is assessed based on unique clinical descriptions of severity for each AE, and these criteria may be different from those used for the assessment of AE seriousness. An AE assessed as Grade 4 based on the NCI-CTCAE grades may or may not be assessed as serious based on the seriousness criteria.

9.2.4. Causality Assessment

The Investigator should assess causal relationship between an AE and the study drugs on the basis of his/her clinical judgment and the following definitions. The causality assessment must be made based on the available information and can be updated as new information becomes available.

Related:

- The AE follows a reasonable temporal sequence from study drug administration, and cannot be reasonably explained by (eg, disease under study, concurrent diseases, and concomitant medications).

or

- The AE follows a reasonable temporal sequence from study drug administration, and is a known reaction to the drug under study or its chemical group, or is predicted by known pharmacology.

Not Related:

- The AE does not follow a reasonable sequence from study drug administration, or is a known reaction to the drug under study or its chemical group, or is predicted by known pharmacology (eg, disease under study, concurrent diseases, and concomitant medications).

9.2.5. Action Taken Regarding Study Drug(s)

Dose Not Changed: No change in study drug dosage was made.

Drug Withdrawn: The study drug was permanently stopped.

Dose Reduced: The dosage of study drug was reduced.

Drug Interrupted: The study drug was temporarily stopped.

Not Applicable: Subject died, study treatment had been completed prior to reaction/event, or reaction/event occurred prior to start of treatment.

9.2.6. Other Action Taken for Event

None.

- No treatment was required.

Medication required.

Prescription and/or over-the-counter medication was required to treat the AE.

Other.

9.2.7. Adverse Event Outcome

Recovered/Resolved

- The subject fully recovered from the AE with no residual effect observed.

Recovering/Resolving

- The AE improved but has not fully resolved.

Not Recovered/Not Resolved

- The AE itself is still present and observable.

Recovered/Resolved with Sequelae

- The residual effects of the AE are still present and observable.
- Include sequelae/residual effects.

Fatal

- Fatal should be used when death is a direct outcome of the AE.

Unknown

9.3. Adverse Events of Special Interest

9.3.1. QTc Prolongation, Torsades de Pointes, and Other Ventricular Arrhythmias

Subjects who experience >480 ms QTcF prolongation and undergo dose interruption and/or reduction must be monitored closely with ECGs, performed twice weekly for the first week of the QTcF prolongation and then weekly thereafter until the QTcF prolongation is resolved, as described in Section 5.4.1.

Grade 3, either serious or non-serious and whether or not causally related, must be recorded as AE or SAE in the Electronic Data Capture (EDC) system within 24 hours of awareness of the central ECG laboratory reading, with the Investigator's assessment of seriousness, causality, and a detailed narrative.²⁴

9.3.2. Concurrent Elevations of Aminotransferases and Bilirubin

Concurrent elevations of aminotransferases and bilirubin, either serious or non-serious and whether or not causally related, meeting the laboratory criteria of ALT or AST $\geq 3 \times$ ULN with simultaneous total bilirubin $\geq 2 \times$ ULN should always be recorded as an AE or SAE within 24 hours of awareness, with the Investigator providing a narrative.²⁴

Subjects will be monitored as described in Section 17.1.

9.4. Safety Reporting Procedure For Investigators

All AEs, including SAEs, and Events of Special Interest will be reported in EDC.

The following types of events should be reported by the Investigator in EDC within 24 hours of awareness:

SAEs (see Section 9.2.2 for definition)

Grade 3, either serious or non-serious and whether or not causally related (see Section 5.4.1 for additional monitoring details)

Hepatic events meeting criteria of ALT or AST $\geq 3 \times$ ULN with simultaneous total bilirubin $\geq 2 \times$ ULN, serious and whether or not causally related (see Section 5.4.2 for additional monitoring details)

All events (serious and non-serious) must be reported with Investigator providing a narrative summarizing the course of the event, including its evaluation, treatment, and outcome should be provided. Specific or estimated dates of event onset, treatment, and resolution should be included when available. Medical history, concomitant medications, and laboratory data that are relevant to the event should also be summarized in the narrative. For fatal events, the narrative should state whether an autopsy was or will be performed, and include the results if available. Source documents (including medical reports) will be retained at the study site and should not be submitted to the Sponsor for SAE reporting purposes.

Urgent safety queries must be followed up and addressed promptly. Follow-up information and response to non-urgent safety queries should be combined for reporting to provide the most complete data possible within each follow-up.

See Section 15.10.1.4 for contact information for SAE reporting. Please call the local SAE Hotline (see Study Manual) or your study monitor for any questions on SAE reporting.

9.5. Notifying Regulatory Authorities, Investigators, and Institutional Review Board/Ethics Committee

Daiichi Sankyo and/or CRO will inform Investigators, Institutional Review Boards/Ethics Committees (IRBs/ECs), and regulatory authorities of any Suspected Unexpected Serious Adverse Reactions (SUSARs) occurring in other study sites or other studies of the investigational drug, as appropriate per local reporting requirements. Daiichi Sankyo and/or CRO will comply with any additional local safety reporting requirements.

Unless otherwise specified, the Investigator (or designee) is responsible for the safety and efficacy of the study drug, unless delegated to the Sponsor, it is the Investigator's responsibility to ensure that the study drug is administered in accordance with the protocol and to report any adverse events to the Sponsor.

9.6. Exposure In Utero During Clinical Studies

Women of childbearing potential must have negative serum pregnancy test results at times specified in the Schedule of Events (Section 17.3). If required by local regulations, additional pregnancy tests will be performed. Serum pregnancy tests will be performed at the local laboratory.

Daiichi Sankyo must be notified of any subject who becomes pregnant while receiving or within 6 months of discontinuing the study drug.

Although pregnancy is not technically an AE, all pregnancies must be followed to conclusion to determine their outcome. This information is important for both drug safety and public health concerns. It is the responsibility of the Investigator, or designee, to report any pregnancy in a female subject using the Exposure In Utero (EIU) Reporting form. Please contact your study monitor to receive the EIU Reporting Form upon learning of a pregnancy. The Investigator should make every effort to follow the subject until completion of the pregnancy and complete the EIU Reporting Form with complete pregnancy outcome information, including normal delivery and induced abortion. The adverse pregnancy outcome, either serious or non-serious, should be reported in accordance with study procedures. If the outcome of the pregnancy meets the criteria for immediate classification as a SAE (ie, post-partum complications, spontaneous or induced abortion, stillbirth, neonatal death, or congenital anomaly, including that in an aborted fetus), the Investigator should follow the procedures for reporting SAEs outlined in Section 9.4.

9.7. Clinical Laboratory Evaluations

The following items will be measured. For clinical laboratory parameters, the reference range of the institution that performs the measurements will be used.

Information will be entered in the CRF on whether measured, date of measurement, and measurement results for the following items:

1. Hematology tests

Red blood cell count, Hgb, hematocrit, white blood cell count, differential white blood cell count (neutrophils, lymphocytes, monocytes, eosinophils, basophils), and platelet count.

2. Serum chemistry tests

Total protein, albumin, albumin/globulin ratio, total bilirubin, direct bilirubin, AST, ALT, alkaline phosphatase, gamma-glutamyl transferase, lactate dehydrogenase, creatine kinase, blood urea nitrogen, creatinine, uric acid, sodium, potassium, chloride, calcium, phosphorus, magnesium, total cholesterol, triglycerides, glucose, and C-reactive protein.

9.8. Vital Signs

Blood pressure and pulse rate will be measured after the subject has rested in a recumbent position for 5 minutes or more.

Information will be entered in the CRF on whether or not measured, date of measurement, and measurement results for the following items:

Systolic blood pressure, diastolic blood pressure, pulse rate, respiratory rate, body temperature, height, and body weight. Height needs to be collected only at Screening and End-of-treatment.

9.9. Electrocardiograms

Triplicate 12-lead ECGs (3 separate ECGs) will be obtained at the times specified in the study schedule (Section 17.3). This will be performed after the subject has rested in a recumbent position for at least 5 minutes. Additional ECGs may be taken at the Investigator's discretion. The triplicate ECGs will be read in a central ECG laboratory, but the ECGs will also be reviewed by a suitably qualified physician at the study site to allow immediate decisions about subject safety. The clinical significance of any ECG change must be assessed by the Investigator. Whether or not measurement was performed, date performed, results, and findings will be recorded in the CRF.

In Part 1 and Part 2 (excluding DDI substudy) pharmacokinetic time-matched ECG will be collected at pre-dose and 3 hours post-dose on Cycle 1/Days 1, 15, and 22, and then on Day 1 of Cycles 2 to 6.

In Part 2 (DDI substudy) pharmacokinetic time-matched ECG will be at 0, 1, 2, 4, and 6 hours on Cycle 1/Day 1; for baseline; pre-dose and 1, 2, 4, and 6 hours post-dose on Cycle 1/Days 1 and 28, Cycle 2/Days 1 and 14). Pharmacokinetic time-matched ECGs will be collected at pre-dose and 3 hours post-dose on Days 14, 15, and 22 of Cycle 1 and Day 1 of Cycles 3 to 6.

9.10. Physical Examinations

A complete physical examination (including ECOG performance status) will be performed at Screening to establish a baseline for study entry, and at additional times specified in the study schedule (Section 17.3). Whenever possible, the same individual will perform subsequent examinations to identify changes from baseline. Symptom-directed physical examinations will be performed at the Investigator's discretion and will include weight determination and a review of body systems.

9.11. Other Examinations

Not applicable.

10. OTHER ASSESSMENTS

Not applicable.

11. STATISTICAL METHODS

11.1. General Statistical Considerations

The primary objective of this study is to assess the safety and tolerability of milademetan in combination with quizartinib and establish RDE in subjects with FLT3-ITD mutant AML.

Final data analysis for the clinical study report will occur at the end of the study when all subjects have either completed the End-of-study Follow-up or discontinued from the study or have received at least 6 months of therapy. However, the ongoing subjects deriving clinical benefit may continue to receive the treatment.

Descriptive statistics will be provided for selected demographic, safety, efficacy, PK, and available exploratory pharmacodynamic data from both dose escalation and dose expansion by dose cohort and visit as appropriate. Descriptive statistics on continuous data will include means, medians, standard deviations, minimum and maximum (as well as geometric means and geometric coefficient of variation for C_{max} and AUC_{24h}), while categorical data will be summarized using frequency counts and percentages. Graphical summaries of the data may be presented.

Assessments of change from baseline to post-treatment or the ratio of post-treatment to baseline will include only those subjects with both baseline and post-treatment measurements. The last non-missing value of a variable taken before the first dose of study drug will be used as the baseline value, unless otherwise specified. In general, missing or dropout data will not be imputed for the purpose of data analysis, unless otherwise specified.

Safety analyses will be performed based on the Safety Analysis Set. Analysis of PK parameters will be based on the PK Analysis Set. Efficacy endpoints will be analyzed based on the Full Analysis Set. Data will be summarized overall (combining subjects treated at the RDE in the dose escalation and dose expansion).

A detailed Statistical Analysis Plan (SAP) describing the methodology to be used in the final analysis will be prepared and finalized before database lock. Statistical methods described within this document may be changed based on advances in research.

11.2. Analysis Sets

The following analysis sets will be defined in this study.

Enrolled Analysis Set will include all subjects who sign the ICF.

Safety Analysis Set (and Full Analysis Set) will include all subjects who received at least 1 dose of milademetan or quizartinib.

DLT Evaluable Set will include all subjects enrolled in the dose escalation who had a DLT within Cycle 1 (28 days) on the study, or without DLT but received at least 75% scheduled dose of milademetan and quizartinib and completed the Cycle 1 evaluation.

PK Analysis Set will include all subjects in the Safety Analysis Set who have sufficient plasma concentration data to characterize PK profile.

11.3. Study Population Data

Disposition and reasons for ending the treatment and discontinuing from the study will be summarized and listed for subjects in the Full Analysis Set.

Demographic and baseline characteristics such as age, sex, race, baseline ECOG performance status, histology, cancer stage, best response to prior chemotherapy, lines of prior regimens, and prior treatment type will be summarized for the Enrolled Analysis Set, Full Analysis Set, and Safety Analysis Set. If 2 analysis sets within a part of the study are identical to each other, the table will be presented only once.

Study drug exposure, treatment duration, and compliance with study therapy will be summarized using descriptive statistics for the Safety Analysis Set.

11.4. Efficacy Analyses

The secondary endpoints of efficacy will include the rates of CR, CRi, CRc, MLFS, PR, SD, ORR, and DOR, according to Investigator's assessment (Section 2.4.3, Section 17.4, and Section 17.5). Transplantation rate and transfusion independence will be based on data reported by study sites. Stable disease rate will be summarized when SD has persisted for at least 3 months. Additionally, CRh rate will be evaluated separately from the other response criteria. The efficacy endpoints will be listed and summarized using descriptive statistics based on the FAS by dose cohort for dose escalation and dose expansion.

For response rates (CRc, ORR, etc), point estimates and 2-sided 95% exact binomial confidence intervals will be provided. Time to event endpoint (DOR) will be summarized descriptively using the Kaplan Meier method.

11.5. Pharmacokinetic/Pharmacodynamic/Biomarker Analyses

11.5.1. Pharmacokinetic Analyses

Pharmacokinetic analyses will be performed on the PK Analysis Set. Plasma concentration-time data for milademetan, quizartinib, and AC886 will be listed, plotted, and summarized using descriptive statistics by dose cohort at each timepoint. Pharmacokinetic parameters (C_{max}, AUC_{24h}, time to reach maximum plasma concentration [T_{max}], trough plasma concentration [C_{trough}]) will be calculated for each subject as possible. The PK parameters will be listed and summarized using descriptive statistics by dose cohort and study day.

In the DDI substudy of 12 subjects in the dose expansion part, C_{max} and AUC_{24h} for milademetan, quizartinib, and AC886 will be calculated and summarized on Cycle 1/Day 1 (milademetan only), Cycle 1/Day 28 (quizartinib, and AC886 only), Cycle 2/Day 1, and Cycle 2/Day 14.

Effects of quizartinib after repeated doses on single dose milademetan PK (C_{max} and AUC_{24h}) will be assessed by analysis of variance (ANOVA) model where reference and test treatments for milademetan PK will be Cycle 1/Day 1 and Cycle 2/Day 1, respectively. The effect of milademetan after repeated doses on steady-state quizartinib and AC886 PK (C_{max} and AUC_{24h}) will also be evaluated using an ANOVA model where the reference and test treatments for quizartinib and AC886 PK will be Cycle 1/Day 28 and Cycle 2/Day 14, respectively. The PK parameters will be transformed prior to analysis using a natural logarithm-transformation.

The 90% confidence intervals for the ratios of the geometric means for the PK parameters (C_{max} and AUC_{24h}) will be calculated.

A population PK model may be developed to assess the PK of milademetan and quizartinib/AC886. The relationship between PK and clinical response defined as the key primary and secondary endpoints may be assessed. The population PK and efficacy response analyses may be reported separately from the clinical study report.

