Quizartinib is a substrate for CYP3A and P-glycoprotein (P-gp). The clinical data suggest that P-gp plays a minimal role in the absorption or clearance of quizartinib. Therefore, no dose adjustment is required when quizartinib is co-administered with a P-gp inhibitor or a P-gp inducer. However, a dose adjustment for quizartinib is required if administered concomitantly with a strong CYP3A inhibitor, but not with moderate or weak inhibitors of CYP3A. Quizartinib is neither an inhibitor nor an inducer of CYP3A, and is thus unlikely to inhibit milademetan metabolism. Quizartinib may have the potential to inhibit P-gp *in vivo*.

Milademetan is a substrate for CYP3A and P-gp. A Phase I study in healthy subjects was conducted to evaluate the effect of co-administration of strong CYP3A inhibitors (itraconazole and posaconazole) on milademetan PK (DS3032-A-U107). Co-administration of milademetan 100 mg with itraconazole 200 mg at steady state increased milademetan mean maximum plasma concentration (C_{max}) and area under the plasma concentration-time curve up to infinity (AUC_{inf}) by 8% and 115%, respectively. Similarly, posaconazole 200 mg at steady state increased milademetan mean C_{max} by approximately 19% and AUC_{inf} by approximately 149%. Therefore, it is recommended that the milademetan dose be reduced by half when it is concomitantly administered with a strong CYP3A inhibitor.

Milademetan is likely a moderate or weak inhibitor of both CYP3A and P-gp. Milademetan is expected to result in minimal change in quizartinib pharmacokinetics (PK) based on the *in vitro* and *in vivo* assessment of drug-drug interaction (DDI) potential. However, the *in vivo* DDI potential between quizartinib and milademetan through P-gp inhibition needs to be evaluated in a clinical study.

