treatment. The substudy will include administration of milademetan alone on Cycle 1/Day 1 only, quizartinib administered alone (Days 15 to 28) of each cycle and concomitant administration of quizartinib and milademetan (Days 1 to 14) of each cycle as shown in Figure 8.1. Pharmacokinetic samples will be collected as shown in Table 8.3. The PK parameters (C_{max} and AUC_{24h}) for milademetan, quizartinib, and AC886 will be assessed to evaluate the effects of (1) steady-state quizartinib on single dose milademetan PK and (2) repeated doses of milademetan on steady-state PK of quizartinib and AC886. The effect of quizartinib on milademetan will be assessed by the comparison of Treatment A: milademetan single dose (C1D1) to Treatment C: milademetan single dose + quizartinib multiple dose (C2D1). The effect of milademetan on quizartinib will be assessed by the comparison of Treatment B: quizartinib multiple dose (C1D28) to Treatment D: quizartinib multiple dose + milademetan multiple dose (C2D14). ECGs will be measured at approximately the same time each day starting at Day 1; to capture the circadian rhythm in ECG for an estimate of time-
ECG measurements are at pre-dose (or Hour 0), 1, 2, 4 and 6 hours post-dose.

Figure 8.1: PK Substudy Design (Part 2) with Milademetan QD 14/28 Schedule

Cycle 1					Cycle 2		
Day -2	Day -1	Day 1	Day 14	Day 28	Day 1	Day 14	
	DS-3032 PK				DS-3032 PK	DS-3032 PK	DS-3032 PK
				Quizartinib PK	Quizartinib PK	Quizartinib PK	Quizartinib PK
ECG	ECG			ECG	ECG	ECG	ECG
	DS-3032b dose: QD x 14d				DS-3032b dose: QD x 14 d		
		Quizartinib dose: QD x 28d			Quizartinib dose: QD x 28d		

PK= pharmacokinetics, QD = once daily.

Table 8.3: PK Substudy Timepoints

Cycle 1									
Day 1 (milademetan only)									
Hour Post-dose	Pre-dose ^a	0.5 ^b	1 ^b	2 ^b	3 ^b	4 ^c	6 ^c	8 ^c	24 ^c
Day 28 (quizartinib, AC886)									
Hour Post-dose	Pre-dose ^a	0.5 ^b	1 ^b	2 ^b	3 ^b	4 ^c	6 ^c	8 ^c	24 ^c
Cycle 2									
Day 1 (milademetan, quizartinib, AC886)									
Hour Post-dose	Pre-dose ^a	0.5 ^b	1 ^b	2 ^b	3 ^b	4 ^c	6 ^c	8 ^c	24 ^c
Day 14 (milademetan, quizartinib, AC886)									
Hour Post-dose	Pre-dose ^a	0.5 ^b	1 ^b	2 ^b	3 ^b	4 ^c	6 ^c	8 ^c	24 ^c

^a Within 1 hour prior to drug administration.

^b ± 5 min.

^c ± 10 min.

For PK samples corresponding to ECG measurements, blood samples should be collected within 10 min after ECG measurement.

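### If quizartinib lowers milademetan clearance, the planned single-dose Cmax and AUC24h ratios will show only part of the change

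*Combined protocol and SAP*

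**What the plan says.** Section 11.5.1 sets the milademetan comparison: "Effects of quizartinib after repeated doses on single dose milademetan PK (C_{max} and AUC_{24h}) will be assessed by analysis of variance (ANOVA) model", in which "reference and test treatments for milademetan PK will be Cycle 1/Day 1 and Cycle 2/Day 1, respectively". The reference is the milademetan-alone day. I read it as Day −1, as in section 6.3.3.2 and Figure 8.1; the minus sign does not appear in the text of 8.1 and 11.5.1. Section 8.1 describes the effect as that of "steady-state quizartinib on single dose milademetan PK" and limits the unaccompanied dose to one day: "The substudy will include administration of milademetan alone on Cycle 1/Day 1 only". Table 8.3 samples both days to 24 h, after which the next dose is given.

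Cmax and AUC24h are analysed on the log scale by ANOVA, with 90% confidence intervals for the geometric mean ratios and no stated no-effect limits. Milademetan Cmax and AUC24h are also calculated and summarized on Cycle 2/Day 14, but do not enter the comparison. Modelling is optional: "A population PK model may be developed to assess the PK of milademetan and quizartinib/AC886".

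Section 1.1 reports an interaction study of milademetan with strong CYP3A inhibitors. Itraconazole "increased milademetan mean maximum plasma concentration (C_{max}) and area under the plasma concentration-time curve up to infinity (AUC_{inf}) by 8% and 115%, respectively". Posaconazole "increased milademetan mean C_{max} by approximately 19% and AUC_{inf} by approximately 149" per cent. The same section says that quizartinib does not inhibit or induce CYP3A, that it is therefore unlikely to slow milademetan metabolism, and that the open question is P-gp.

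**The concern.** After one dose, a fall in clearance hardly moves the peak and raises the curve mainly in its later part. An area cut at 24 h captures only some of that rise. The sponsor's own inhibitor data show the pattern for this drug: AUCinf more than doubled while Cmax rose 8% and 19%. The substudy keeps Cmax but replaces AUCinf by a 24 h area.

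Under the 14/28 schedule, subjects take milademetan daily for 14 days per cycle. With linear kinetics, the daily area at steady state equals the single-dose AUCinf, so AUCinf is the quantity that describes repeated dosing. If clearance falls, the planned ratios are biased towards no effect. A ratio near 1.2 or 1.3 could be reported as a minor interaction when repeated-dose exposure has risen by much more.

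**Working it through.** **Plan's own figure.** There is none. The documents give no expected ratio or precision for this comparison, and section 11.10 says that the DDI sample size was practical.

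**Inputs.** From the documents: single dose, 24 h sampling, and the inhibitor ratios for Cmax and AUCinf (1.08 and 2.15; 1.19 and 2.49). Assumed: one-compartment linear model, ka = 0.7/h, half-life 3 to 24 h, volume and bioavailability F unchanged.

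**Formulas**, in units of F × dose / volume, with k = ln 2 / half-life:

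- AUC24h = ka/(ka − k) × [(1 − e^(−24k))/k − (1 − e^(−24ka))/ka]
- AUCinf = 1/k
- C(t) = ka/(ka − k) × (e^(−kt) − e^(−ka·t)), with Cmax at t = ln(ka/k)/(ka − k)

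Halving clearance replaces k by k/2, so the AUCinf ratio is exactly 2.0.

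**Worked case, half-life 12 h.** k = 0.05776.

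- Alone: 0.7/0.64224 × (0.75/0.05776 − 1/0.7) = 1.0899 × (12.984 − 1.429) = 12.59
- With clearance halved: 0.7/0.67112 × (0.5/0.02888 − 1/0.7) = 1.0430 × (17.312 − 1.429) = 16.57
- AUC24h ratio: 16.57/12.59 = 1.32

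**Results for a true ratio of 2.0:**

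| Half-life alone (h) | AUC24h ratio | Cmax ratio | 24 h concentration ratio | AUC beyond 24 h, alone | AUC beyond 24 h, test day |
|---|---|---|---|---|---|
| 3 | 1.86 | 1.21 | 12.8 | 1% | 7% |
| 4 | 1.75 | 1.18 | 6.9 | 2% | 14% |
| 6 | 1.57 | 1.14 | 3.6 | 7% | 27% |
| 12 | 1.32 | 1.09 | 1.9 | 27% | 52% |
| 20 | 1.19 | 1.06 | 1.5 | 46% | 68% |
| 24 | 1.16 | 1.06 | 1.4 | 52% | 72% |

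With ka from 0.5 to 2/h and half-life 6 to 20 h, the AUC24h ratio is 1.19 to 1.59 and the Cmax ratio 1.03 to 1.17.

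**Cross-check against section 1.1.** If the inhibitors act on clearance alone, each pair of ratios fixes ka/k: 16.6 for itraconazole and 5.4 for posaconazole. With an assumed Tmax of 2 to 4 h, the half-lives are 7.7 to 15.4 h and 3.6 to 7.3 h. A halved clearance then gives AUC24h ratios of 1.48 to 1.25 and 1.80 to 1.48. The two pairs disagree, so they do not settle the half-life.

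**If F changes instead.** Doubling F multiplies every concentration by two, so AUC24h and Cmax ratios are both 2.0. Mixed effects fall between: at 12 h and ka = 1/h, F up 1.41-fold with the rest from clearance gives an AUC24h ratio of 1.65.

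**Interval.** With 12 complete pairs and an assumed within-subject CV of 30%, the 90% limits lie a factor exp(1.796 × 0.2936 × √(2/12)) = 1.24 either side. An observed 1.2 would have limits 0.97 to 1.49, which include 1 and exclude the true 2.0.

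**The case against.** The strongest objection is mechanism. Itraconazole and posaconazole are strong CYP3A inhibitors, and section 1.1 says quizartinib is not one. A reader might infer that any doubling of milademetan exposure would be seen as 1.2 to 1.6. The documents do not support that: a rise through gut P-gp would appear in full. This stands and makes the point conditional. It does not remove it, because section 1.1 does not confine the P-gp question to the gut, and an unlikely effect is still one that an interaction substudy should be able to measure.

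Three other strong readings also fail:

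- *That Cycle 2/Day 14 is unused.* It is summarized. It is only outside the ANOVA, where it has no milademetan-alone repeated-dose day to pair with.
- *That the plan cannot separate absorption from clearance.* Diverging AUC24h and Cmax ratios, and the 24 h concentrations already to be listed and summarized, give a partial indication. They do not size the clearance change.
- *That most of the rise always falls after 24 h.* At a 6 h half-life, 53% of it falls within 24 h in this model.

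The consequence is also limited. No dosing rule or no-effect limit depends on the interval, the substudy serves a secondary endpoint, and Part 1 chooses the dose from subjects already on the combination (section 3.1.2). The separate SAP promised in sections 11.1 and 11.11 could add detail. But section 11.5.1 already names the parameters and the contrast, and AUCinf is not among them.

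**Conclusion.** The concern holds in conditional form. If quizartinib lowers milademetan clearance, the two planned ratios are biased towards 1. For a true doubling from halved clearance, AUC24h would show about 1.6 to 1.2 and Cmax about 1.14 to 1.06, for half-lives of 6 to 20 h. At 3 to 4 h the AUC24h loss is modest (1.86 to 1.75).

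These sizes rest on a one-compartment linear model, ka of 0.7/h and a half-life that the documents do not give. The direction of the bias does not depend on the exact values. For an effect through absorption there is no such bias.

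A reader might also infer that the milademetan conclusion should rest on Cycle 2/Day 14 AUC24h divided by milademetan-alone AUCinf. In the linear model this ratio returns 1.98 to 2.00 for a true 2.0. But section 1.1 describes milademetan as a CYP3A and P-gp substrate and a likely moderate or weak inhibitor of both. Any self-inhibition by Day 14 would be credited to quizartinib, so the documents do not support it as the main estimate.

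**What to change.** Keep the Cmax and AUC24h ratios and describe them as first-dose effects. Add to section 11.5.1, from samples already scheduled:

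1. Within-subject ratios, Cycle 2/Day 1 to the milademetan-alone day, of the 24 h concentration and, where estimable, of AUCinf, each with a 90% confidence interval. Report the percentage of AUCinf extrapolated on each day.
2. A commitment (*will* in place of *may*) to estimate the ratio of milademetan CL/F with and without quizartinib, with a 90% confidence interval, from a population PK model fitted to all DDI-substudy profiles including Cycle 2/Day 14. This is the estimate to use when the extrapolated area is large.
3. Cycle 2/Day 14 AUC24h over milademetan-alone AUCinf as supportive only, with the self-inhibition caveat stated.

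AUCinf and CL/F from oral data combine clearance and bioavailability. They size the total change and should be read with the Cmax and 24 h concentration ratios when mechanism is discussed.

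The cost is a few derived parameters and a small population PK fit, with no new visits or samples. The main weakness is that AUCinf may be heavily extrapolated if the half-life is long: at 12 h with clearance halved, 27% on the reference day and 52% on the test day.
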